## PROTOCOL SYNOPSIS

Primary Objectives:	Define the accuracy of $^{68}\text{Ga}$ -PSMA-11 PET-CT for detecting the location and size of clinically significant prostate cancer lesions in low and intermediate risk disease.
Secondary Objectives:	Evaluate how knowledge of the PSMA-PET might inform treatment planning.
Exploratory Objectives:	Generate pilot data to be validated in larger studies
Study Design:	Prospective, early phase clinical trial, single arm
Test Factor/Exposure:	Intravenous injection of $^{68}\text{Ga}$ -PSMA-11 and detection with PET-CT scanner
Duration of Treatment:	Patients will undergo injection of $^{68}\text{Ga}$ -PSMA-11 PET-CT and pre-treatment MRI scan and followed until biopsy and/or surgical resection.
Enrollment:	Subject accrual is planned for 24 months
Inclusion Criteria:	
 
1. <math>\geq 18</math> years of age
 
2. Must provide written informed consent
 
3. Presence of low or intermediate risk prostate cancer or at risk of having intermediate risk cancer 
 
a. Intermediate risk prostate cancer: 
 
i. Grade group 2 = 3 + 4, or
 
ii. Grade group 3 = 4 + 3
 
 
 
b. At Risk of intermediate risk prostate cancer: 
 
i. 4K score <math>\geq 20\%</math>, or
 
ii. Select MDx <math>\geq 20\%</math>, or
 
iii. PSA Density <math>\geq 0.15</math>
 
iv. Grade group 1 = 3+3
 
 
 
 
 
4. Scheduled for MRI or has recently completed SOC MRI (within 6 months) for further biopsy, surgical removal or focal therapy.
 
5. Willing and able to lie still for approximately 50 minutes in an enclosed space for the CT
 

[figure not shown]
Exclusion Criteria:	
 
1. Participation in another investigational trial involving research exposure to ionizing radiation concurrently or within 30 days.
 
2. Does not meet safety criteria for MRI scan (e.g. metal implant that is not allowed).
 
3. Significant acute or chronic medical, neurologic, or illness in the subject that, in the judgment of the Principal Investigator, could compromise subject safety, limit the ability to complete the study, and/or compromise the objectives of the study.
 

Number of Subjects:	36 patients
Number of Sites:	Indiana University Simon Cancer Center, Indiana University Health Hospital, IU Health North, IU Health North medical office building, IU Health Methodist Hospital
Primary Outcome:	
Sextant based analyses using prostatectomy whole-mount analysis or biopsy as Gold Standard:
 
 
1) Sensitivity, specificity, Receiver operator curve (ROC) of mpMRI for each Gleason pattern (3, 4, 5)
 
2) Sensitivity, specificity, ROC of PSMA PET-CT for each Gleason pattern (3, 4, 5)
 

Secondary Outcomes:	
 
1. Lesion based analysis of accuracy
 
2. For 3+4: Sensitivity and specificity of mpMRI based on Gleason %pattern 4
 
3. For 3+4: Sensitivity and specificity of PET-CT based on Gleason %pattern 4
 
4. Sensitivity and specificity for extra-capsular extension (mpMRI vs PET-CT)
 
5. Sensitivity and specificity for seminal vesicle invasion (mpMRI vs PET-CT)
 
6. Impact of PSMA PET-CT on treatment plan for surgery: 
 
a. Additional lesions found, additional sextants involved, extra-capsular extension detected, seminal vesicle invasion detected, lymph node invasion detected.
 
 
 
7. Impact of PSMA PET-CT on treatment plan for biopsy: 
 
a. Additional lesions found, additional sextants involved
 
 
 

## 2 SCHEMA

While the total N=36 for this trial, the number of subjects enrolled on each arm (prostatectomy vs. surveillance) is not required to be divided evenly.

## 3 BACKGROUND

### 3.1 Background & Preliminary Work

Up to 60% of men in the U.S. unwittingly have Gleason 6 (pure pattern 3: 3+3) prostate cancer by their 80s on autopsy, which argues for active surveillance of this tumor (Zlotta, et al. 2013). Long-term active surveillance cohorts demonstrate low (<5%) 15-year metastasis rates (Musunuru, et al. 2017). However, <50% choose active surveillance when diagnosed on biopsy with Gleason 6 prostate cancer (Womble, et al. 2015). This is due to multiple factors: (1) prostate cancer is multi-focal in >80%; (2) prostate cancer commonly has mixed grade lesions; and (3) conventional imaging modalities (US, MRI) miss significant cancer. There is also disagreement on what follow-up is needed during active surveillance. Molecular imaging agents would bring assurance and peace of mind to hundreds of thousands of men, if they are capable of selectively detecting clinically significant prostate cancer (Gleason patterns 4 and 5). *We expect to determine whether the PSMA-targeted PET agent, Ga-PSMA-11, reliably detects significant prostate cancer and what minimum percentage Gleason pattern 4 is required for detection by comparison of PET/MR to whole mount analysis.*

Multiparametric 3-T MRI has shown the ability to locate prostate cancer lesions that are higher grade and increased size. For example, MRI-targeted biopsy increases the detection of clinically significant prostate cancer using fewer cores than template biopsy (Pokorny, et al. 2017, Wysock, et al. 2014), while reducing detection of insignificant Gleason 6. However, recent studies mapping MRI lesions to final whole-mount pathology show limitations. For example, a recent study showed only 80% of index (largest) tumors were seen by MRI and even fewer clinically significant non-index lesions (Le, et al. 2014). Another recent study showed MRI missed a clinically significant lesion in 26% of patients using whole-mount analysis (Borofsky, et al. 2017). Fittingly, Borofsky titled their paper, “What are we missing? False negative cancers at Multiparametric MR imaging of the prostate.” MRI interpretation has also been shown to vary substantially across radiologists, which persisted after correcting for radiologist practice volume (Son, et al. 2017). Therefore, the majority of urologists still take ultrasound-based template biopsies at the time of MRI guided biopsy (MRI-ultrasound fusion).

The status quo for pathologic assessment is Gleason Grading, which combines the two dominant Gleason patterns and sometimes lists a tertiary pattern. Gleason grading might be sufficient when treating the whole gland: surgery, radiation, cryotherapy, etc. However, conventional Gleason grading gives insufficient detail when considering active surveillance or focal therapy because the Gleason grade combines all the lesions into a

single score and is not lesion specific. For example, a prostate with three cancer lesions might be reported as Gleason 3 + 4 (90%/10%) on final pathology while the individual lesions are: (1) 3 + 4 + 5 (30%/60%/10%), (2) 3 + 4 (90%/10%), (3) 3 + 3.

Lesion (1) is clinically significant while lesion (3) is not. Lesion (2) is of debatable significance and requires further study. Certainly, the above 3-lesion cancer is different than a single lesion 3+4 cancer despite the same grading. A detailed lesion-specific analysis is required to accurately assess new imaging agents and ultimately to test the paradigm of focal organ-sparing therapy. *The proposed research is innovative, in our opinion, because we perform lesion and intra-lesion specific analyses while testing Ga-PSMA-11 with PET-CT. This requires researchers with experience in lesion specific prostate cancer pathology, mpMRI and PET imaging, and focal therapy.* Finally, we feel the study design is innovative because it incorporates PSMA PET-CT imaging into the standard clinical workflow. This enables pilot data using the current standard-of-care as the control; the goal is to facilitate translation of molecular imaging more quickly to clinical care.

Whole mount pathologic analysis of PET imaging in prostate cancer has been reported primarily out of Germany. No prospective trials were found combining PSMA, PET-CT, and whole-mount analysis. Furthermore, studies have focused on high-risk disease rather than low/intermediate risk. For example, a retrospective trial out of Germany (Eiber, et al. 2016) combined Ga-PSMA-11 and PET-CT and found improvement in Receiver operator curve (ROC) for PET-CT over MRI (0.73 to 0.88, p<0.001). Of the 53 patients, 53% were high risk. The authors concluded prospective studies were warranted for biopsy guidance. Recently, F-FACBC (Fluciclovine) was used with PET-CT and compared to MRI for biopsy guidance in a prospective clinical trial (Jambor, et al. 2017). F-FACBC had high sensitivity (87%), but low specificity (56%) resulting in a low ROC (0.72). F-FACBC is not specific for prostate cancer resulting in replacement with PSMA-based tracers in clinical practice.

[figure not shown]
The Urology-Radiology-Pathology team at Indiana University has been employing fusion biopsy since 2013 and has performed more than 600 during this time. A recent abstract presented at the annual meeting of the American Urologic Association in 2017 demonstrated 22% of index lesions (largest tumor) were missed by MRI ([name], et al. 2017), and MRI undersized the index cancer lesion when compared to final pathology (2.2cm vs. 1.9cm, p = 0.03). A tracer that is both more sensitive and specific is desired leading urologists to continue ultrasound template biopsies with MRI targeted biopsy.

The Ga-PSMA-11 (HBED-CC) radiopharmaceutical (Eder, et al. 2014; Eiber, et al. 2015, Afshar-Oromieh, et al. 2015) is structurally based on a class of urea-derived inhibitors of PSMA (Pillai, et al. 2016). The targeting peptide has been modified at its N-terminus to incorporate the HBED-CC chelating agent with an exceptionally high binding affinity (~1039) for the Ga3+ ion (Figure 1 and Table 1). Methods for on-demand

production of  $^{68}\text{Ga}$ -PSMA-11 are already established (IND # 131,806), based on our research use of this radiopharmaceutical in imaging patients with recurrent prostate cancer.

**Table 1.** PSMA Affinities of the PSMA-11 Agent Before, and After,  $\text{Ga}^{3+}$  Chelation

PSMA Ligand	IC50 (nM)
PSMA-11 HBED-CC	$5.7 \pm 0.5$
Ga-PSMA-11 HBED-CC	$6.1 \pm 0.8$

[figure not shown]
**Figure 1.** Structure of the PSMA-11 (HBED-CC) conjugate employed in preparation of the  $^{68}\text{Ga}$ -PSMA-11 radiopharmaceutical. The PSMA-11 has a molecular weight of 947 g/mol. The radiopharmaceutical synthesis protocol for on-demand production of  $^{68}\text{Ga}$ -PSMA-11 employs 10- $\mu\text{g}$  of the PSMA-11 conjugate per batch.

The project investigators have significant experience in PET with  $^{68}\text{Ga}$ -PSMA-11. Our initial human experience with  $^{68}\text{Ga}$ -PSMA-11 PET was in performing patient imaging for dosimetry assessment, studying ten prostate cancer patients with biochemical recurrence who had been previously clinically imaged with  $^{11}\text{C}$ -acetate under an Expanded Access IND (Green, *et al.* 2017). The expected utility of  $^{68}\text{Ga}$ -PSMA-11 PET was apparent even in that limited series, with  $^{68}\text{Ga}$  detection of sites of metastasis that were not apparent in  $^{11}\text{C}$ -acetate imaging (Figure 2). We have subsequently dropped  $^{11}\text{C}$ -acetate imaging in prostate cancer patients with biochemical recurrence in favor of  $^{68}\text{Ga}$ -PSMA-11 PET, and have performed clinical imaging on over 100 patients under Expanded Access IND 131,806. When evaluating the first 70  $^{68}\text{Ga}$ -PSMA-11 PET scans, we found improved detection ( $p < 0.05$ ) over  $^{11}\text{C}$ -acetate PET at PSA-values  $> 2$  (abstract accepted to America Urologic Association 2018 national meeting).

We have also recently completed a prospective clinical trial evaluating  $^{68}\text{Ga}$ -PSMA-11 whole-body PET-CT in 10 patients with biopsy-proven high-risk prostate cancer. The PET-CT was obtained prior to scheduled surgical resection for correlation of imaging

[figure not shown]
findings with whole-mount pathology. These subjects also received a second  $^{68}\text{Ga}$ -PSMA-11 dose intraoperatively to allow *in vitro* high-resolution PET assessment of tracer binding within the resected tissue. All staging  $^{68}\text{Ga}$ -PSMA-11 PET/CT scans showed suspicious prostate lesions with median (IQR) of 10.6 SUV (8-14); benign prostate had a median (IQR) of 3.8 SUV (3-5). Four staging  $^{68}\text{Ga}$ -PSMA-11 PET-CT scans showed seminal vesicle invasion, and two showed nodal involvement; all were confirmed on final pathology.

Indiana University performed >1,000 robotic prostatectomies over the past four years and >600 MRI-fusion biopsies during the same span. This clinical volume will provide adequate numbers for trial accrual (n=36). There are currently no competing trials for our study population. The investigators ([name], [name]) and clinical trial coordinator ([name]) will identify patients in the Indiana University urology clinic and inclusion/exclusion criteria will be assessed prior to informed consent

**Figure 2:**  $^{68}\text{Ga}$ -PSMA-11 PET/CT demonstrated avid lymph nodes (A) and bony metastasis (B) not seen with the  $^{11}\text{C}$ -acetate PET/CT. The PSA was 1.7 and 11.1, respectively. During the recent clinical trial, a PET-CT scanner was installed at Indiana University allowing us to compare PET-CT to PET-MRI (Figure 3). MRI has far superior soft-tissue contrast compared to the CT, which cannot identify the lesions within the prostate gland by itself, and cannot qualify as a “one-stop-shop” examination. Integrated utilization of PSMA PET and MRI has paramount implications for the improved diagnostic pathway of the prostate cancer. In addition to the better diagnostic potential, there is also a potential for significantly reduced cost of the total diagnostic workup of the prostate cancer using a single examination (i.e., PSMA PET-CT) compared to having a mpMRI, PSMA PET study, and a bone scan. We hypothesize the improved

soft tissue resolution will improve biopsy accuracy and surgical planning when compared to PET-CT.

**Figure 3:** The PET-CT (A) shows much more soft tissue detail within the prostate when compared to the PET-CT (B) on the same patient.

### 3.2 Rationale

Our long-term goal is to improve cancer outcomes and quality of life for prostate cancer patients by bringing novel imaging agents and systems to the diagnosis and treatment of prostate cancer. The overall objective of this Early Phase Clinical Trial is to begin defining the accuracy of  $^{68}\text{Ga}$ -PSMA-11 for detecting the location and size of clinically significant prostate cancer lesions in low and intermediate risk disease.

The proposed studies will be performed with a state-of-the-art Vision PET-CT system which offers unprecedented spatial resolution and counting sensitivity for a clinical PET system that make it ideal for supporting biopsy and focal therapy decisions. We propose detailed intra-lesion whole-mount pathologic analysis as the gold standard for critically assessing PSMA PET accuracy in patients undergoing surgery, and blinded PSMA PET-CT comparison with standard multi-parametric MRI (mpMRI) for patients having biopsy on active surveillance. This intensive testing of the accuracy and value of PSMA-based tracers requires our unique collaboration of surgeons, radiologists, pathologists, and imaging scientists with decades of experience and innovation.

## **4 STUDY OBJECTIVES**

### **4.1 Primary**

Define the accuracy of  $^{68}\text{Ga-PSMA-11}$  PET-CT for detecting the location and size of clinically significant prostate cancer lesions in low and intermediate risk disease.

### **4.2 Secondary**

Evaluate how knowledge of the PSMA-PET can inform treatment planning.

### **4.3 Exploratory**

Generate pilot data for future larger clinical trials

## **5 ELIGIBILITY CRITERIA**

### **5.1 Inclusion Criteria**

To be considered eligible to participate in this study, a patient must meet all the inclusion criteria listed below:

1.  $\geq 18$  years of age
2. Must provide written informed consent

3. Presence of low or intermediate risk prostate cancer or at risk of having intermediate risk cancer
  - a. Intermediate risk prostate cancer:
    - i. Grade group **2** = 3 + 4, or
    - ii. Grade group **3** = 4 + 3
  - b. At Risk of intermediate risk prostate cancer:
    - i. 4K score  $\geq$  20%, or
    - ii. Select MDx  $\geq$  20%, or
    - iii. PSA Density  $\geq$  0.15
    - iv. Grade group 1= 3+3
- Note:** Where multiple cancer lesions are present on biopsy, it is allowable to have Gleason 8 or 9 cancer lesions if they are in addition to the intermediate risk cancer as described above.
4. Scheduled for MRI or has recently completed SOC MRI (within 6 months) for further biopsy, surgical removal, or focal therapy.
5. Willing and able to lie still for approximately 50 minutes in an enclosed space for the CT.

## 5.2 Exclusion Criteria

1. Participation in another investigational trial involving research exposure to ionizing radiation concurrently or within 30 days.
2. Does not meet safety criteria for MRI scan (e.g. metal implant that is not allowed).
3. Significant acute or chronic medical, neurologic, or psychiatric illness in the subject that, in the judgment of the Principal Investigator, could compromise subject safety, limit the subject's ability to complete the study, and/or compromise the objectives of the study.

## 6 PATIENT REGISTRATION

Patient enrollment will take place over 24 months at a single institution – Indiana University Simon Cancer Center (IUSCC) encompassing Indiana University Hospital (IUH), IU Health North, IU Health North medical office building, IU Health Methodist Hospital. Potential patients will be identified in the Urology clinic, or by physician referrals, mostly likely but not exclusively during pre-operative consultations for biopsy or surgical removal of prostate cancer. All study procedures will take place at IUSCC/IUH/IU-Health Methodist Hospital, with the research imaging performed at the IU Health Goodman Hall outpatient facility. All patients will be registered with the Indiana University (IU) Department of Urology. Regulatory files will be maintained by the Department of Urology. Applicable regulatory documents must be completed and on file

prior to registration of any patients. Patients who appear to be eligible for this trial will undergo the Informed Consent Process and be screened for eligibility utilizing the Eligibility Criteria. Individual patient registration will be done in the REDCap database. The original signed Institutional Review Board (IRB) approved Informed Consent Document and completed eligibility checklist will be stored in the following location: Indiana University Department of Urology, [name].

## 7 STUDY PROCEDURES

### 7.1 Summary

This patient population will have low (**1** = Gleason 3 + 3) or intermediate risk (**2** = 3 + 4; **3** = 4 + 3) prostate cancer, or be at risk of having intermediate disease as evidenced by a 4K score  $\geq 20\%$ , or Select MDx  $\geq 20\%$ , or PSA Density  $\geq 0.15$ . Patients will be scheduled for a MRI as part of routine care for either surgical planning or for further biopsy. Following the informed consent process, patients who enroll in the study will receive a  $^{68}\text{Ga}$ -PSMA-11 PET study along with their standard of care (SOC) MRI on an PET-CT. If the Vision PET-CT is not available, a standard PET-CT and SOC MRI can be done with co-registration of PET and MRI done using software to generate the equivalent of the PET-CT images. Patients receiving SOC MRI guided biopsy will have the additional PET data factored into their guided biopsy plan. The sensitivity and specificity for lesion characterization will be evaluated, along with the ability of the tracer to inform the treatment planning. Patients receiving surgical removal of the prostate will have a slice-by-slice whole mount analysis to assess the sensitivity and specificity the PSMA PET.

## 7.2 Study Calendar

	Screening/ Baseline (-180 days)	Biopsy if indicated	Imaging	Surgery if indicated
REQUIRED ASSESSMENTS				
Informed Consent	X			
Inclusion/Exclusion	X			
Medical History 	X			
PSMA dose and PET scan			X 	
SOC MRI				
SOC MRI-guided biopsy		X		
SOC PET-guided biopsy		X		
SOC Focal Therapy				X
Pathologic assessment of biopsy		X		
SOC prostatectomy				X
Pathologic assessment of whole mount				X

Footnotes:

1. Medical history may be obtained via medical records, as necessary.
2. A second  $^{68}\text{Ga}$ -PSMA-11 PET, approximately 6-12 months following initial scan may be requested, if: (1) the subject undergoes HIFU treatment and/or (2) during follow-up, is rescheduled for MRI-fusion biopsy as standard of care.

## 7.3 Assessments by Visit

### 7.3.1 Baseline/Screening (within 6 months of scan(s)/biopsy):

- Informed consent: investigators or their designees will discuss with subjects the nature of the study, its requirements, risks, and restrictions to obtain informed consent for participation in the study. Subjects should have sufficient time to review the study information and consent form and to ask any questions necessary to make an informed decision regarding their participation in the study. Written informed consent is to be obtained before any other study-specific procedure.
- Eligibility criteria: make sure patient meets study eligibility criteria.
- Demographics: track sex, race, ethnicity, date of birth, address, etc.
- Medical history: includes past medical history, past surgical history, allergies, any ongoing medical conditions, and including medications noted in patients record at time of screening

### 7.3.2 Imaging

- Eligibility criteria: ensure subject continues to meet study eligibility (if longer than 60 days since screening)
- Medical history: capture additional medical history since screening (if longer than 60 days since screening)
- Concomitant medications: record medications taken since screening through day of surgery (if longer than 60 days since screening)
- There will be a  $\geq 4$  week wait period between prior biopsy and protocol related MR imaging to allow for resolution of hematomas.
- $^{68}\text{Ga}$ -PSMA-11 PET-CT and mpMRI:

- Patient receives a ~3-5 mCi dose of Ga-PSMA-11. (A physician-sponsored IND has been successfully obtained)
- Patient will undergo research Vision PET-CT and SOC MRI at Goodman Hall (or similar facility) which is anticipated to last approximately 60 minutes. Per our institutional standard of care, patients will receive intravenous iodinated contrast with the PET-CT unless medically contraindicated.
- Imaging Protocol for Ga-PSMA-11 PET Data Acquisition (approximate times):

Time (minutes)	Activity
- 60	Patient arrives, and completes consent forms, while radiopharmaceutical synthesis and quality control procedures are completed.
0	Administer  Ga-PSMA-11, 3-5 mCi (outside the camera).
5-50	Start standard-of-care pelvic MR acquisition with simultaneous collection of  Ga-PSMA-11 PET.
50-55	Patient can leave camera and depart.

- The PET read will be done by a board certified nuclear medicine specialist (e.g. [name] or similar) and the MRI read will be done by a board certified MR radiologist (e.g. [name] or similar). Suspicious lesions will be marked in a blinded fashion.
- AE assessment: AEs will be assessed at the time of Ga-PSMA-11 administration and also at the appointment for biopsy (if done) any event not expected is collected including but not limited to: rash and shortness of breath.
- Safety monitoring following radiopharmaceutical administration will consist of visual and verbal monitoring of the patient after injection, and during and at the conclusion of the PET/CT procedure, with any apparent patient abnormalities, reactions or reported effects noted in the study records.
- The nuclear medicine technologists administering the radiopharmaceutical are responsible for immediately reporting any adverse or unexpected events to the principal investigator or clinical

designee, who will report the occurrence of any adverse events to the IRB.

- As in most clinical nuclear medicine procedures, these radiopharmaceuticals are administered at a sub-pharmacologic doses. Adverse events are exceedingly unlikely, as Ga-HBED-CC has been clinically employed, extensively and without reported incident, in clinical patient diagnostic imaging studies in prostate cancer patients in Germany and other European countries, as well as in over 100 patients locally.
- If there is a discrepancy between the PSMA and conventional MRI scan, the investigators will discuss the treatment plan with the patient at the investigator's discretion.
- If the patient does not undergo a prostatectomy, no further study procedures will be performed.
- If the Vision PET-CT is not available, a standard PET-CT and mpMRI may be done with software registration of PET and MR images.
- A patient may have a second Ga-PSMA-11 PET, approximately 6-12 months following initial scan, if: (1) the patient undergoes HIFU treatment and/or (2) during follow-up, is rescheduled for MRI-fusion biopsy as standard of care.

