### **7.3.3 PET, MRI Biopsy:**

- Patients proceeding to surgery following PSMA PET and MRI may forgo biopsy.
- Patients not proceeding to surgery will undergo a SOC MRI-fusion biopsy based on the pre-biopsy scan detailed in 7.3.2. PET findings will be integrated into the planning of the fusion biopsy. See appendix C for details of the fusion biopsy.
- AE assessment: AEs will be assessed at the time of Ga-PSMA-11 administration and also at the appointment for biopsy (if done) any event not expected is collected including but not limited to: rash and shortness of breath.
- A sextant-based analysis will be performed. See appendix D for details of sextant analysis.
- A secondary “per lesion” analysis will also be performed.

- How the knowledge of the PSMA-PET informs treatment will be tracked. Examples of informing the decision include PSMA-PET detected additional intraprostatic cancer lesions diagnosed.

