## 9.4 Study Endpoints

### 9.4.1 Primary

Sextant based analyses using prostatectomy whole-mount analysis or biopsy as Gold Standard (Appendix D):

- Sensitivity, specificity, Receiver operator curve (ROC) of mpMRI overall and for each Gleason pattern (3, 4, 5)
- Sensitivity, specificity, ROC of PSMA PET-CT overall and for each Gleason pattern (3, 4, 5)

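### A PET-MRI discrepancy may change who reaches whole mount, so whole-mount sensitivity and specificity can be biased; the pathway intended before PET should be recorded and used in a sensitivity analysis

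*Combined protocol and SAP*

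**What the plan says.** Section 7.1 describes the route before PET: "Patients will be scheduled for a MRI as part of routine care for either surgical planning or for further biopsy". After both scans are read, Section 7.3.2 provides: "If there is a discrepancy between the PSMA and conventional MRI scan, the investigators will discuss the treatment plan with the patient". This is left to the investigator's discretion.

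The final pathway then sets the reference standard. For surgery, Section 7.1 says: "Patients receiving surgical removal of the prostate will have a slice-by-slice whole mount analysis to assess the sensitivity and specificity the PSMA PET". Section 7.3.3 adds: "Patients proceeding to surgery following PSMA PET and MRI may forgo biopsy". For the rest, it says: "Patients not proceeding to surgery will undergo a SOC MRI-fusion biopsy based on the pre-biopsy scan detailed in 7.3.2", and "PET findings will be integrated into the planning of the fusion biopsy". Section 2 leaves the split open: "the number of subjects enrolled on each arm (prostatectomy vs. surveillance) is not required to be divided evenly".

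The primary endpoint (9.4.1) accepts either whole mount or biopsy as the reference in one sextant analysis. Section 9.7 estimates sensitivity and specificity by GEE, compares PET with MRI by McNemar's test and compares AUCs by bootstrap. It has no term for the type of reference and no analysis set based on the pathway intended before PET. The baseline items in 7.3.1 do not include that pathway. Blinded lesion marking (7.3.2) protects the reads, not the later choice of treatment.

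**The concern.** Section 3.2 presents whole mount as the reference for critically assessing PET in men having surgery. If some men reach surgery because PET showed something that MRI did not, that group is partly selected on the result of the test under evaluation. Discrepant pairs trigger the discussion in 7.3.2, and discrepant pairs are also what McNemar's test counts.

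This is a separate matter from the weakness of biopsy as a reference. Reporting whole-mount results on their own, the usual remedy for a mixed reference, would not remove the selection, because the whole-mount group is where it acts. A PET-MRI contrast there could mix accuracy with the decision to operate. Without a record of the plan before PET, nobody could tell afterwards whether this happened or in which direction.

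**Working it through.** **The plan's own figure.** Section 9.3 assumes 6 sextants per man and 40% prevalence, so 6 × 0.40 = 2.4 cancer sextants per man, and N = 1.96² × Se(1 − Se) / d² / 2.4. For Se 0.80 and d 7.5%, this gives 109.3 / 2.4 = 45.5, so 46 as stated. Six of the eight cells reproduce exactly; the two cells of 27 compute to 26 (25.6). The tolerated error of 7.5-10 points is a yardstick for what follows.

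**Inputs for the selection check.** From 9.3: six independent sextants, prevalence 0.40. Assumed, because the documents give no figures: both scans have sensitivity 0.75 and specificity 0.90 and err independently; a share π of men (25-50%) is planned for surgery before PET; a share r (25-75%) of the other men with at least one PET-only sextant is re-routed to surgery.

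**Men with a PET-only sextant.**
- Cancer sextant: P(PET+, MRI−) = 0.75 × 0.25 = 0.1875.
- Benign sextant: P(PET+, MRI−) = 0.10 × 0.90 = 0.09.
- Any sextant: 0.40 × 0.1875 + 0.60 × 0.09 = 0.129.
- At least one of six: 1 − 0.871⁶ = 0.563.
- At least one of the other five: k = 1 − 0.871⁵ = 0.499.

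**Probability that the man qualifies for re-routing, jointly with the scan result.**
- Cancer sextant, any result: 0.1875 + 0.8125k = 0.593. With PET positive: 0.1875 + 0.5625k = 0.468. With MRI positive: 0.75k = 0.374.
- Benign sextant, any result: 0.09 + 0.91k = 0.544. With PET negative: 0.90k = 0.449. With MRI negative: 0.09 + 0.81k = 0.494.

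**Whole-mount group.** Let w = (1 − π)r. PET sensitivity = (0.75π + 0.468w) / (π + 0.593w). MRI sensitivity replaces 0.468 by 0.374. PET specificity = (0.90π + 0.449w) / (π + 0.544w). MRI specificity replaces 0.449 by 0.494. Example with π = 0.25, r = 0.50, w = 0.375: PET sensitivity = (0.1875 + 0.1755) / 0.472 = 0.769, and MRI sensitivity = (0.1875 + 0.1403) / 0.472 = 0.694.

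| π | r | Sensitivity PET / MRI (%) | Gap (points) | Specificity PET / MRI (%) |
|---|---|---|---|---|
| 0.50 | 0.25 | 75.5 / 73.5 | 2.0 | 89.1 / 90.1 |
| 0.25 | 0.50 | 76.9 / 69.4 | 7.5 | 86.6 / 90.4 |
| 0.25 | 0.75 | 77.3 / 68.2 | 9.1 | 85.9 / 90.5 |

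Men planned for surgery before PET return 75% and 90% for both scans.

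**Other directions.** If a discrepancy of either kind re-routes men equally, the formulas for PET and MRI coincide: sensitivity is 73-75% and specificity 89-90% for both. A patient-level model with both scans at 0.80/0.80 and a baseline surgery probability of 0.5 shows the range:
- PET-only raises surgery to 0.7 and MRI-only lowers it to 0.3. Cancer cases selected: 0.64 × 0.5 + 0.16 × 0.7 + 0.16 × 0.3 + 0.04 × 0.5 = 0.50. PET sensitivity is (0.32 + 0.112) / 0.50 = 0.864; MRI sensitivity is (0.32 + 0.048) / 0.50 = 0.736. Specificities mirror these (0.736 and 0.864), so Youden is 0.60 for both.
- PET-only lowers surgery to 0.3, others at 0.5. PET sensitivity is 0.368 / 0.468 = 0.786; MRI sensitivity is 0.40 / 0.468 = 0.855.

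In a sextant-level simulation at 0.80/0.80, the two AUCs stayed within 0.001 of each other under every rule tried.

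**Pooled primary estimate.** Suppose biopsy finds a share β of cancer sextants (assumed). Re-routing then matters only through cancer that biopsy would have missed. The gap is w(1 − β) × 0.1875(1 − k) / T, where T is the share of cancer sextants found by either reference. At π = 0.25, r = 0.75, β = 0.90: T = 0.583 + 0.90 × 0.417 = 0.958, and the gap is 0.5625 × 0.10 × 0.094 / 0.958 = 0.55 points, the largest value over the range. At β = 0.80 the same setting gives 0.5625 × 0.20 × 0.094 / 0.917 = 1.15 points.

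**The case against.** A reader might infer that whole-mount entry does depend on PET and that whole-mount accuracy therefore favours PET. The documents support neither step. Section 7.3.2 says only that the plan is discussed, and the discrepancy may be in either direction. The plan could stay as it was, or move to another biopsy target or to focal therapy. Section 7.3.3 excuses surgical patients from biopsy; it re-routes nobody. Section 7.3.4 ties surgery to clinical indication. An intended route usually exists before PET: inclusion criterion 4 and Section 7.1 both link the MRI to planned surgery or biopsy. Where PET gains sensitivity in the working it loses specificity, and AUC need not move. These arguments stand, and they limit the point to a possible dependence of unknown direction.

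Three further arguments carry weight. No whole-mount-only comparison is prespecified; the primary endpoint pools both references, and Section 9.7 calls the PET-MRI comparison hypothesis generating. The assumed re-routing is strong: 0.563 × 25-75% means that 14-42% of men not planned for surgery would switch. And making the planned-surgery men the main whole-mount set would be costly. In the setting π = 0.25, r = 0.50, about 36 × (0.25 + 0.375 × 0.563) = 16.6 men reach whole mount, but only 9 were planned. The 95% half-width on 75% sensitivity, 1.96 × √(0.1875 / 2.4n), grows from 13 to 18 points. That supports a sensitivity analysis, not redefined arms.

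What these arguments do not answer is the missing record. The protocol expects PET to affect plans, since it tracks this (7.3.3, 7.3.4) and lists it among the secondary endpoints (9.4.2). Yet nothing fixes the plan before PET for use in the analysis.

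**Conclusion.** The point holds as a possible bias, not a demonstrated one. The protocol allows the PET result to influence which reference standard a man receives, and the analysis plan has no means to detect or handle this.

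If PET-only findings lead to surgery, whole-mount sensitivity would favour PET by about 2-9 points with equally accurate scans, with PET specificity 1-5 points below MRI. The upper end is comparable with the 7.5-10 points of error tolerated in Section 9.3. These figures rest on assumed accuracies, independent errors and assumed rates of planned surgery and re-routing. Under symmetric re-routing the PET-MRI difference is zero, and if PET-only findings make surgery less likely it reverses. The pooled primary estimate is little affected: under 1 point if biopsy finds 90% of cancer sextants, and about 1 point at 80% in the most extreme setting.

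One inconsistency bears on this. Section 7.3.2 ends study procedures for a patient who has no prostatectomy, while Section 7.3.3 gives such patients a fusion biopsy and a sextant analysis. Read literally, the former leaves only the surgical group verified, and the protection from pooling is lost. The two sections must be reconciled.

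**What to change.** 1. Add one REDCap field at registration, completed before any PET result is disclosed: intended pathway (prostatectomy, biopsy/surveillance, focal therapy).
2. In Section 9.7, report whole-mount sensitivity and specificity of PET and MRI for all men with whole mount. Add a prespecified sensitivity analysis restricted to men whose recorded plan before PET was prostatectomy, and show men re-routed to surgery after PET as a separate row.
3. Use the same field as the baseline for the treatment-plan impact endpoints in Section 9.4.2.
4. Reconcile Sections 7.3.2 and 7.3.3 on what follows for men without prostatectomy.

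The cost is one data item and a smaller, less precise subset (9 instead of about 17 men in the example above), which is why it belongs in a sensitivity analysis. The field must be completed prospectively, because a plan not recorded before disclosure cannot be reliably reconstructed. Enrolment and clinical care are unchanged.
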